4.6.4 Vital Signs

A summary table and a patient listing of the following vital signs parameters will be provided for Safety Population:

- Systolic blood pressure (SBP)
- Diastolic blood pressure (DBP)
- Heart rate
- Temperature.

A summary table of vital sign abnormalities will be provided by treatment group in Safety Population.

4.6.5 Growth

The continuous growth will be analyzed through the analyses of weight and height for patients in Safety Population. Growth (height) velocity will be explored. In primary CSR, growths from study beginning to 24 weeks after the end of treatment/principal observation period will be reported.

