8.2.5.3 Safety Data Analysis

The primary safety analysis will compare safety in Group A with Group B *at 24 weeks post-end of treatment/end of untreated observation*. The safety data of Group A and Group B will be qualitatively evaluated alongside subjects in Group C and the switch arm.

- *Incidence, nature, and severity of serious and non-serious AEs (including neurological and psychiatric events)*
- *Reasons for the discontinuation of any study medication*
- *Dose modifications for laboratory abnormalities and clinical AEs*
- *Changes in vital signs and laboratory tests from screening/baseline, including thyroid function*
- *Effect on growth (height and weight)*

The following safety outcome measures will be assessed using descriptive statistics at 1, 2, 3, 4, and 5 years post-end of treatment:

- *Incidence, nature, and severity of persisting AEs, new-onset related SAEs/ non-serious AEs of special interest*
- *Changes in thyroid function from screening/baseline*
- *Effect on growth (height and weight)*

AEs: AEs will be assigned preferred terms and categorized into body systems according to the Medical Dictionary for Regulatory Activities (MedDRA) classification of the World Health Organization (WHO) terminology. Descriptive statistics will be used to summarize safety parameters by group. Neurological and psychiatric AEs will be assessed in further detail, including persistence and duration, as well as new onset of SAEs and non-serious AEs of special interest related to PEG-IFN reported during the extended long-term follow-up period of this study.

Laboratory Safety Data: The laboratory data (including thyroid function) will be analyzed according to Roche's "International Guideline for the Handling and Reporting of Laboratory Data".

Growth (weight and height): The continuous growth will be analyzed with Residual Maximum Likelihood, or analysis of covariance. The assumptions of the analysis such as normally distributed residuals will be assessed. If necessary, rectifying transformations shall be applied. Growth (height) velocity will be explored.

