4.6.5.1 Definitions

The primary endpoints for assessing treatment effects on growth are actual values at visit and their changes from baseline in (1) height (weight, BMI) for age percentile; (2) height (weight, BMI) for age z-score.

For the current analysis, the gender-specific Centers for Disease Control and Prevention (CDC) Growth Charts for 2000 (Kuczmarski et al. 2000) will be used as reference to calculate the height (weight, BMI) for age percentile and height (weight, BMI) for age z-score.

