4.6.5.2 Summary of Growth Measurements

All growth variables will be listed by treatment group and center/patient number in Safety Population, including raw height (weight, BMI) measurements at each visit, height (weight, BMI) for age z-scores and height (weight, BMI) for age percentiles (actual value and change from baseline).

Descriptive summaries of the z-scores and percentiles for height, weight and BMI for age (actual value and change from baseline) for patients in Safety Population will be presented by visit.

Patients with height (weight, BMI) for age percentile drop ($\geq 15\%$) from baseline will be summarized and listed by treatment group in Safety Population.

Plots of the mean (and 95% CI) of z-score and percentile for height, weight and BMI for age by treatment group in Safety Population will be depicted from the study baseline to 24 weeks after the end of treatment/principal observation period.

Plots of the mean change from the baseline (and 95% CI) of z-score and percentile for height, weight and BMI for age by treatment group in Safety Population will be depicted from the study baseline to 24 weeks after the end of treatment/principal observation period.

Individual change from baseline plots of z-score and percentile for height, weight and BMI for age by group will be depicted.

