Switch Population: The switch population shall be those subjects randomized to Group B who opt to switch to initiating treatment with PEG-IFN after Week 48.

Group C: Subjects who have advanced fibrosis (diagnosed on liver biopsy) will receive PEG-IFN in an advanced fibrotic arm (Group C).

Efficacy

- The primary efficacy analysis will compare efficacy in Group A with Group B. Subjects with missing values will be considered as non-responders. The efficacy data of Group A and Group B will be qualitatively evaluated alongside subjects in Group C and the Switch arm.
- The primary analysis of the response rate variables will be with the Cochran-Mantel-Haenszel test (χ^2) stratified by genotype (A versus non-A) and ALT (< and $\geq 5 \times$ ULN). Fisher's exact test will be used as a secondary analysis. The response rates for HBeAg seroconversion will be analyzed at the end of the initial 24-week follow-up period.
- Several secondary analyses are planned, including descriptive statistics of secondary endpoints, and exploratory p-values between Group A and Group B.

Safety

- The primary safety analysis will compare safety in Group A with Group B. The safety data of Group A and Group B will be qualitatively evaluated alongside subjects in Group C and the Switch arm.
- Adverse events: AEs will be assigned preferred terms and categorized into body systems according to the Medical Dictionary for Regulatory Activities (MedDRA) classification of the World Health Organization (WHO) terminology. Descriptive statistics will be used to summarize safety parameters by group. Neurological and psychiatric AEs will be assessed in further detail, including persistence and duration, as well as new onset of SAEs and non-serious AEs of special interest related to PEG-IFN reported during the extended long-term follow-up period of this study.
- Laboratory Safety Data: The laboratory data will be analyzed according to Roche's "International Guideline for the Handling and Reporting of Laboratory Data".
- Growth (weight and height): The continuous growth will be analyzed with residual maximum likelihood, or analysis of covariance. The assumptions of the analysis such as normally distributed residuals will be assessed. If necessary rectifying transformations shall be applied. Growth (height) velocity will be explored.

Pharmacokinetic

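### SAP 4.6.5 drops, without a stated reason, the protocol's REML or ANCOVA analysis of growth, so the SAP body plans no treated-minus-untreated estimate or confidence interval

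*SAP*

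**What the plan says.** Protocol 8.2.5.3 opens with the purpose: "The primary safety analysis will compare safety in Group A with Group B", timed at 24 weeks after treatment or observation ends. Effect on height and weight is one of the listed components. The method follows: "The continuous growth will be analyzed with Residual Maximum Likelihood, or analysis of covariance", with residual checks and transformation if needed. Growth at Years 1 to 5 is given descriptive statistics only.

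SAP Appendix 1, which reproduces the protocol synopsis, repeats the commitment: "The continuous growth will be analyzed with residual maximum likelihood, or analysis of covariance".

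SAP 4.6.5 reads instead: "The continuous growth will be analyzed through the analyses of weight and height for patients in Safety Population". Section 4.6.5.1 then states an inferential aim, "The primary endpoints for assessing treatment effects on growth are actual values at visit and their changes from baseline in" percentile and z-score for age (height, weight and BMI). Section 4.6.5.2 lists the output:

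- listings by group;
- "Descriptive summaries of the z-scores and percentiles for height, weight and BMI for age", as actual values and changes from baseline (this sentence says by visit and does not mention group);
- a by-group count of patients whose percentile falls by at least 15%;
- plots of group means, and "Plots of the mean change from the baseline (and 95% CI) of z-score and percentile for height, weight and BMI for age by treatment group";
- individual change plots.

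Height velocity is to be explored, with no method named.

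**The concern.** The protocol (Section 1.2) names transient growth suppression among the adverse effects that seem more prominent in children than in adults. Section 3.1.1.1 justifies the untreated arm as allowing a direct comparison of efficacy and safety. Growth is an outcome for which that arm is especially needed, because children grow whether treated or not.

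The SAP body sets out to assess treatment effects on growth but plans two separate group trajectories, each with its own interval. No contrast between them is pre-specified or printed. A reader of the report would have to judge a known pediatric harm by eye or work out the difference unaided. The SAP body also departs from the protocol, and from its own appendix, without saying so.

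**Working it through.** **1. Is the model elsewhere in the SAP?** SAP Section 4 says that all A-versus-B analyses are in 4.3 to 4.6, so 4.6.5 is where a growth model belongs. SAP Section 1 assigns table, listing and figure layouts to DAP Module 2 and data specification to Module 3; neither is described as holding methods. The only mention of REML or ANCOVA is in Appendix 1.

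**2. Group sizes.** The documents give no sample size, SD or power for growth. The only planning figure is 145 randomized patients at 2:1 (32% versus 10%, two-sided 0.05, at least 80% power). The two-proportion formula with continuity correction gives 48 + 96 = 144, which agrees with 145. Splitting 145 at 2:1 gives 97 in A and 48 in B.

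**3. Precision of the missing estimate.** Assumption: SD of change in z-score is 0.3 to 0.5. Half-width of the 95% interval = 1.96 × SD × √(1/nA + 1/nB).

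| Groups | √(1/nA + 1/nB) | SD 0.3 | SD 0.5 |
|---|---|---|---|
| 97 : 48 | 0.1765 | 0.10 | 0.17 |
| 97 : 24 (half of B switched, assumed) | 0.2280 | 0.13 | 0.22 |

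The second row applies to follow-up Week 24. Eligible Group B patients may start PEG-IFN at any time from Week 48 for one year (Protocol 4.8 and 5.3), and SAP 4.4.1.1 expects some to do so before follow-up Week 24. The documents do not say how many.

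**4. ANCOVA against a change-score difference.** With equal variances and baseline-to-follow-up correlation r, the ratio of standard errors (change score to ANCOVA) is √(2/(1 + r)).

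- r = 0.90: √(2/1.90) = 1.03
- r = 0.95: √(2/1.95) = 1.01

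So the change score costs 1 to 3%. At r = 0.5 the ratio would be √(2/1.5) = 1.15. These correlations are assumptions.

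**5. Reading two group intervals instead.** With equal SDs, two 95% intervals fail to overlap only when |z| for the difference exceeds 1.96 × (1/√97 + 1/√48)/√(1/97 + 1/48) = 1.96 × 0.2459/0.1765 = 2.73. The two-sided error rate is then about 0.006. Where a direct test has 80% power, the overlap rule has Φ(2.80 − 2.73), about 53%.

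**The case against.** The strongest reply is that Appendix 1 is part of the SAP and nothing in 4.6.5 withdraws it, so the REML or ANCOVA commitment remains. That stands in part. A reader might infer that the sponsor deliberately abandoned the model, or that no growth effect can be estimated under this SAP. The documents support neither. They show an SAP whose body and appendix disagree, and the body is what sets out the planned output.

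A reader might also infer that baseline is ignored. It is not: changes from baseline in age- and sex-referenced z-scores and percentiles are planned endpoints, and only regression adjustment is absent. Setting ANCOVA against raw visit values would make the gain look large, but change scores are the relevant comparator, and against them the gain is small.

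Nor are separate group intervals invalid. Independent group means and intervals allow an unadjusted difference to be derived, and judging by overlap is conservative. The defect is that the contrast is not pre-specified or reported, and that overlap can miss a real effect.

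The protocol also says that safety parameters will be summarized descriptively by group. But it names a model for growth in the same section and reserves descriptive statistics alone for growth at Years 1 to 5, so the general sentence does not cancel the specific one.

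Finally, a follow-up Week 24 contrast is not clean. Switchers are no longer untreated controls. Because only patients without seroconversion are offered the switch, the controls who remain are a selected group. This stands, and the fix must deal with it.

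**Conclusion.** The point holds as an unexplained omission and an internal inconsistency. SAP 4.6.5 leaves out the growth model stated in Protocol 8.2.5.3 and SAP Appendix 1, and the SAP body provides no between-group difference or interval for a component of the primary A-versus-B safety comparison.

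The loss is the estimate itself, which would be informative: a half-width of about 0.10 to 0.17 z-score units at 97:48, and 0.13 to 0.22 at follow-up Week 24 if half the controls had switched. These figures rest on an assumed SD of change and an assumed switching fraction, neither of which the documents give. Baseline adjustment in itself adds little at high correlation. The primary efficacy analysis is unaffected. The change should be made because growth is a recognized pediatric safety outcome and the data are already scheduled.

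**What to change.** In SAP 4.6.5.2, specify a REML repeated-measures model of height and weight for age z-score with group, visit, group-by-visit and baseline z-score, or ANCOVA at each reported visit with group and baseline z-score. Report the A-minus-B difference with its 95% interval at Week 48, the contrast free of switching, and at follow-up Week 24.

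State how Group B measurements after a switch to PEG-IFN are handled. One option is to exclude them from the untreated-control contrast and add a sensitivity analysis by randomized group. If they are excluded, say what is assumed about the missing values, since switching depends on HBeAg status.

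Align 4.6.5 with Protocol 8.2.5.3 and SAP Appendix 1, or state and justify the departure. The protocol names only the method, and only for weight and height, so the terms above are a specification of it. BMI, age and the stratification factors are optional additions.

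The cost is one model-based table and the switch-handling rule. No new data are needed: SAP Appendix 2, Tables 1 and 2, schedules height and weight in both groups at Weeks 12, 24, 36 and 48 and at follow-up Weeks 12 and 24.

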4.6.5.1 Definitions

The primary endpoints for assessing treatment effects on growth are actual values at visit and their changes from baseline in (1) height (weight, BMI) for age percentile; (2) height (weight, BMI) for age z-score.

For the current analysis, the gender-specific Centers for Disease Control and Prevention (CDC) Growth Charts for 2000 (Kuczmarski et al. 2000) will be used as reference to calculate the height (weight, BMI) for age percentile and height (weight, BMI) for age z-score.

4.6.5.2 Summary of Growth Measurements

All growth variables will be listed by treatment group and center/patient number in Safety Population, including raw height (weight, BMI) measurements at each visit, height (weight, BMI) for age z-scores and height (weight, BMI) for age percentiles (actual value and change from baseline).

Descriptive summaries of the z-scores and percentiles for height, weight and BMI for age (actual value and change from baseline) for patients in Safety Population will be presented by visit.

Patients with height (weight, BMI) for age percentile drop ($\geq 15\%$) from baseline will be summarized and listed by treatment group in Safety Population.

Plots of the mean (and 95% CI) of z-score and percentile for height, weight and BMI for age by treatment group in Safety Population will be depicted from the study baseline to 24 weeks after the end of treatment/principal observation period.

Plots of the mean change from the baseline (and 95% CI) of z-score and percentile for height, weight and BMI for age by treatment group in Safety Population will be depicted from the study baseline to 24 weeks after the end of treatment/principal observation period.

Individual change from baseline plots of z-score and percentile for height, weight and BMI for age by group will be depicted.

4.6.6 Child Depression Inventory (CDI)

Child Depression Inventory (CDI) is a questionnaire that has been validated for children ages 7-17 years old to assess a range of depressive symptoms (Kovacs 1992). In primary CSR, CDI scores from study beginning to 24 weeks after the end of treatment/principal observation period will be reported.

A list of patients, with a CDI raw score >19 (with or without an AE of depression) will be provided for Safety Population.

The total T-scores are standardized scores with a mean of 50 and a standard deviation of 10 derived from a normative samples of 1226 Florida public school students (see CDI manual in [Kovacs 1992] for more details).

The total T-score at each visit, and its change from baseline to week 12, 24, 36, 48 during treatment/principal observation period and at week 4 of initial follow-up, will be summarized for Safety Population.

4.7 ANALYSES OF GROUP C

Efficacy analyses and safety analyses from enrollment to 24 weeks after the end of treatment will be reported from all patients in Group C who receive at least one dose of study medication.

The patient major PVs, patient disposition, and patient discontinuation for Group C will be summarized.

Demographics and baseline characteristics, previous and concurrent disease, previous and concomitant Hepatitis B treatment for Group C will be summarized.

The primary efficacy endpoint and all secondary efficacy endpoints will be descriptively summarized for Group C. Continuous secondary efficacy endpoints will be summarized over time. Graphs of continuous secondary endpoints and their corresponding 95% confidence intervals over time will be displayed.

All the safety analyses for Group C will be conducted similarly as the safety analyses performed as described in [Section 4.6](#).

4.8 ANALYSES OF SWITCH ARM

By the clinical cutoff for the primary CSR (24 weeks after the end of treatment period (Group A) or principal observation period (Group B)), very few patients in Switch arm would have completed their 24 week follow-up period after completion of treatment. Hence, only listings of deaths, SAEs, and AEs leading to discontinuation of study treatment will be presented in the primary CSR. All the other efficacy and safety data for Switch arm will be summarized and reported in the final CSR.

4.9 INTERIM ANALYSES

No interim efficacy analyses are planned.

Appendix 1 Protocol Synopsis

SYNOPSIS OF PROTOCOL YV25718, VERSION E

TITLE	A Phase IIIb Parallel Group, Open Label Study of Pegylated Interferon alfa-2a Monotherapy (PEG-IFN, Ro 25-8310) Compared to Untreated Control in Children with HBeAg Positive Chronic Hepatitis B in the Immune Active Phase		
SPONSOR	Hoffmann-La Roche	CLINICAL PHASE	IIIb
INDICATION	Treatment of HBeAg positive chronic hepatitis B (CHB) in children.		
OBJECTIVES	
 • To compare efficacy and safety between a group treated with Pegylated-Interferon Alfa-2a (PEG-IFN) monotherapy and an untreated control group in HBeAg positive children with CHB virus infection in the immune active phase. • To evaluate the pharmacokinetics of PEG-IFN following administration of a new BSA-based dosing regimen in HBeAg positive PEG-IFN treated children with CHB virus infection. 		
TRIAL DESIGN	
 • A 2:1 randomized, controlled, parallel group, open label, multicenter study of PEG-IFN treatment (Group A) compared to an untreated control (Group B). • Subjects without advanced fibrosis and without cirrhosis (assessed by liver biopsy) will be randomized 2:1 to PEG-IFN treatment (Group A) or untreated control (Group B) respectively. That is for every 2 subjects randomized to PEG-IFN only 1 will be randomized to the untreated control. Subjects in Group A will receive PEG-IFN for 48 weeks. • Subjects with advanced fibrosis (assessed by liver biopsy) will be assigned to PEG-IFN treatment (Group C: Advanced Fibrotic arm). Subjects in Group C will receive PEG-IFN for 48 weeks. • The first 48 weeks from randomization will be referred to as the treatment period for Group A and Group C and the principal observation period for Group B. • Forty-eight weeks after randomization, PEG-IFN will be offered to subjects in the Group B untreated control group who have not experienced HBeAg seroconversion. This offer will be available for up to one year following Week 48. If eligible, these subjects will enter the Switch arm and receive PEG-IFN for 48 weeks. • All subjects will be followed up for 5 years after the end of treatment/principal observation period. • Liver elastography will be performed in at least 50 subjects as a site specific sub-study. 		
NUMBER OF SUBJECTS	N = 160		

TARGET POPULATION	
 Children aged 3 to < 18 years of age with CHB, HBeAg+ve, HBsAg+ve, detectable HBV DNA (> 10,000 copies/mL [$> 2,000$ IU/mL]) by PCR and ALT >ULN but $\leq 10 \times$ ULN (using the reference range of the testing laboratory). Liver biopsy needs to have been performed within 2 years prior to baseline, or within 9 months prior to baseline for subjects with advanced fibrosis. Subjects with advanced fibrosis will be assigned to PEG-IFN treatment (Group C), and those without advanced fibrosis or cirrhosis will be randomized. Cirrhotic subjects will be excluded from the study. Subjects co-infected with HCV, HDV, HIV or who have received therapy for hepatitis B in the prior 6 months or who have de-compensated liver disease will be excluded. 												
LOCATION (Regions)	Americas, Europe, Asia-Pacific.												
LENGTH OF STUDY	
 For Group A, Group B non-switch and Group C subjects the study length is 6 years (1 year treatment/principal observation period, 5 years follow-up). For Group B switch subjects the study length is up to 8 years (1 year principal observation period, up to 1 year follow-up whilst deciding whether to switch, 1 year treatment period, 5-year follow-up period). 												
END OF STUDY	
 Primary endpoint is assessed 24 weeks after the end of treatment/principal observation period, with a further 4.5 years of follow-up. End of study is last subject last visit. 												
INVESTIGATIONAL MEDICAL PRODUCT(S) DOSE/ ROUTE/ REGIMEN	
PEG-IFN for 48 weeks subcutaneously once weekly with dosing based on the following BSA categories:
 
  
 Dose (μg)	BSA Range (m^2)	
   
 45	0.51–0.53	
 
 65	0.54–0.74	
 
 90	0.75–1.08	
 
 135	1.09–1.51	
 
 180	>1.51	
  
	Dose (μ g)	BSA Range (m^2)	45	0.51–0.53	65	0.54–0.74	90	0.75–1.08	135	1.09–1.51	180	>1.51
Dose (μ g)	BSA Range (m^2)												
45	0.51–0.53												
65	0.54–0.74												
90	0.75–1.08												
135	1.09–1.51												
180	>1.51												
NON-INVESTIGATIONAL MEDICAL PRODUCT(S)	N/A												
COMPARATOR “DRUG” (or STANDARD OF CARE) DOSE/ ROUTE/ REGIMEN	N/A (Untreated control)												
ASSESSMENTS OF:													
- EFFICACY	
Primary: HBeAg seroconversion (loss of HBeAg and presence of anti-HBe) at 24 weeks post-end of treatment/principal observation period.
 
Secondary:
 
 Loss of HBeAg, HBsAg seroconversion (loss of HBsAg and presence of anti-HBs), loss of HBsAg, quantitative serum ALT, proportion of normal ALT, quantitative HBV DNA, suppression of HBV DNA < 100,000 copies/mL (< 20,000 IU/mL), < 10,000 copies/mL (< 2,000 IU/mL), undetectable and change from baseline, combined endpoint of HBeAg seroconversion and HBV DNA < 100,000 copies/mL (< 20,000 IU/mL), and combined endpoint of HBeAg seroconversion and HBV DNA < 10,000 copies/mL (< 2,000 IU/mL) at the end of treatment/principal observation period, at 24 weeks after end of treatment/principal observation period, and at 1, 2, 3, 4 and 5 years after end of treatment/principal observation period. 												

	
 • Persistence of HBeAg seroconversion (loss of HBeAg and presence of anti-HBe) at the end of treatment/principal observation period, and at 1, 2, 3, 4 and 5 years after end of treatment/principal observation period. • Descriptive change from baseline in liver elasticity (in liver elasticity site specific sub-study subjects) at end of treatment/principle observation period, and at 24 weeks and 2 years after end of treatment/principal observation period.
- SAFETY	
Safety during the treatment/principal observation period and initial 24 weeks of follow-up:
 
 • Serious and non-serious AEs (including neurological and psychiatric events, and non-serious AEs of special interest, and monitoring with neuro-psychiatric questionnaire for PEG-IFN treated subjects). • Laboratory test results (including thyroid function). • Vital signs. • Growth: weight and height. 
Safety during the 4.5 year extended, long-term follow up period:
 
 • All persisting AEs initially reported prior to follow-up Week 24 (including neuro-psychiatric events). • New-onset serious AEs (including neuro-psychiatric events) and non-serious AEs of special interest related to PEG-IFN. • Deaths • Thyroid function. • Growth: weight and height.
- PHARMACOKINETICS/ PHARMACODYNAMICS	
 • Site-specific sub-study • Blood samples will be collected in PEG-IFN treated subjects to evaluate the pharmacokinetics of PEG-IFN following administration of a new BSA-based dosing regimen. • Samples should be collected during weeks 1 and 24 at pre-dose (0 hour) and 24-48, 72-96, and 168 hours post-dose. Additional pre-dose samples should be collected at weeks 4, 8 and 12 within 6 hours prior to administration.
- EXPLORATORY BIOMARKERS	
Optional Roche Clinical Repository (RCR) samples, including plasma and whole blood RNA and whole blood DNA (baseline only), will be taken from consenting/assenting subjects at Baseline, Weeks 12, 24 and 48, 24 weeks after end of treatment/principal observation period, and at 1, 2, 3, 4 and 5 years after end of treatment/principal observation period. These specimens will be used for research purposes, for example to help to better understand the pharmacogenetics, pathogenesis, course and outcome of CHB and related diseases, and identify dynamic biomarkers that are predictive of response to PEG-IFN treatment (in terms of dose, safety and tolerability). These specimen(s) may be stored for up to 15 years after the end of Study YV25718.

INTERIM ANALYSES AND STOPPING RULES	
Individual subject treatment with PEG-IFN must be discontinued in the event of any of the following:
 
 • Severe hypersensitivity reactions (e.g., anaphylaxis, angioedema, bronchoconstriction) • Severe depression • Absolute neutrophil count $< 0.25 \times 10^9$ cells/L or febrile neutropenia • Platelets $< 25 \times 10^9$ cells/L

Discontinuation of individual patient treatment with Pegasys should be considered in the event of any of the following:

- Evidence of hepatic decompensation (e.g., Child-Pugh Class B or C clinical classification [Appendix 2] or clinical evidence such as ascites or varices)
- Thyroid abnormalities that cannot be effectively controlled by medication
- Hypoglycemia, hyperglycemia, or diabetes mellitus that cannot be effectively controlled by medication
- New or worsening visual disorders such as field deficits, decrease or loss of vision
- Persistent or unexplained pulmonary infiltrates or pulmonary function impairment
- Worsening of psoriatic lesion
- Development of autoimmunity, including autoimmune hepatitis
- Pregnancy

A DSMB will review safety data on a routine basis (as per DSMB charter). Enrollment will be suspended and/or the study will be halted if serious concerns about safety are raised pending further analysis and review. Enrollment and/or study re-start will resume only if the DSMB and the sponsor are satisfied with the safety of treatment.

PROCEDURES (Summary):

After signing informed consent/assent and meeting screening parameters, subjects without advanced fibrosis and without cirrhosis (assessed by liver biopsy performed within 2 years prior to baseline) will be randomized 2:1 into the PEG-IFN treatment (Group A) or untreated control (Group B) respectively. Stratification will be performed by genotype (A versus non-A) and ALT ($<$ and $\geq 5 \times$ ULN). Subjects with advanced fibrosis (assessed by liver biopsy performed within 9 months prior to baseline) will be assigned to PEG-IFN treatment (Group C). Subjects in Group A and Group C will receive PEG-IFN for 48 weeks.

Subjects treated with PEG-IFN (Group A and Group C) will be seen for evaluation at Weeks 1, 2, 4, 8, 12 and then every 6 weeks during the treatment period, and during the initial 24 weeks of follow-up at follow-up Weeks 4, 12, and 24.

Subjects in the untreated arm (Group B) will be seen for evaluation at 12 weekly intervals during the principal 48-week observation period and during the initial 24 weeks of the follow-up period.

For consenting/assenting subjects in the site specific liver elasticity sub-study, liver elastography will be performed at baseline, end of treatment/principal observation period, follow-up Week 24, and follow-up Year 2.

Forty-eight weeks after randomization, PEG-IFN will be offered to subjects in the Group B untreated control group who have not experienced HBeAg seroconversion. This offer will be available for up to 1 year following 48 weeks from randomization. If eligible, these subjects will enter the Switch arm, where they will start the Switch schedule of assessments and receive PEG-IFN for 48 weeks.

For consenting/assenting subjects in the site specific PK sub-study, additional visits will also be required for PK blood sampling. When adequate PK data have been collected over the first 24 weeks for at least 15 PEG-IFN-treated subjects, ideally with representation from all BSA categories, exposure will be analyzed and if necessary an adjustment will be made to the dosing regimen. Once PK data up to Week 24/switch Week 24 are available for at least 5 to 10 subjects in each BSA category, subject PK sampling will be stopped. However, the sub-study may be stopped even if data from a minimum of 5 subjects in each BSA category are not obtained in the case of excessively long recruitment times.

Those subjects that do not complete the treatment period should still return for all follow-up visits. As well as evaluation during the initial 24 weeks post-end of treatment/principal observation period, all subjects will be followed up annually for 5 years after the end of treatment/principal observation period. Safety assessments at these extended long-term follow-up visits will include evaluation of persisting AEs which were initially reported prior to follow-up Week 24, assessment of new-onset SAEs (including neuro-psychiatric events) and non-serious AEs of special interest related to PEG-IFN, deaths, thyroid function, and growth (weight and height).

Standard measures will be taken in this study to minimize the pediatric subjects' possible pain and distress.

STATISTICAL ANALYSES

Sample Size

Sample size is based on the χ^2 test statistic. Assuming a 32% HBeAg seroconversion rate for Group A (PEG-IFN) and 10% for Group B (untreated control), a total sample size of 145 subjects provides at least 80% power at the 0.05 level of significance with a two-sided χ^2 test. The sample size shall be increased by 10% and rounded to 160 subjects to allow for advanced fibrotics (Group C) and withdrawals.

Populations

ITT population: For Group A, the ITT population shall include all subjects who receive at least one dose of study drug. For the untreated Group B the ITT population shall include all subjects with at least the baseline efficacy or safety data. For the ITT population subjects will be analyzed according to the groups to which they were randomized.

Subjects in Group B who switched to receive PEG-IFN after Week 48 and prior to 24 weeks post-observation period will be counted as non-responders.

Switch Population: The switch population shall be those subjects randomized to Group B who opt to switch to initiating treatment with PEG-IFN after Week 48.

Group C: Subjects who have advanced fibrosis (diagnosed on liver biopsy) will receive PEG-IFN in an advanced fibrotic arm (Group C).

Efficacy

- The primary efficacy analysis will compare efficacy in Group A with Group B. Subjects with missing values will be considered as non-responders. The efficacy data of Group A and Group B will be qualitatively evaluated alongside subjects in Group C and the Switch arm.
- The primary analysis of the response rate variables will be with the Cochran-Mantel-Haenszel test (χ^2) stratified by genotype (A versus non-A) and ALT (< and $\geq 5 \times$ ULN). Fisher's exact test will be used as a secondary analysis. The response rates for HBeAg seroconversion will be analyzed at the end of the initial 24-week follow-up period.
- Several secondary analyses are planned, including descriptive statistics of secondary endpoints, and exploratory p-values between Group A and Group B.

Safety

- The primary safety analysis will compare safety in Group A with Group B. The safety data of Group A and Group B will be qualitatively evaluated alongside subjects in Group C and the Switch arm.
- Adverse events: AEs will be assigned preferred terms and categorized into body systems according to the Medical Dictionary for Regulatory Activities (MedDRA) classification of the World Health Organization (WHO) terminology. Descriptive statistics will be used to summarize safety parameters by group. Neurological and psychiatric AEs will be assessed in further detail, including persistence and duration, as well as new onset of SAEs and non-serious AEs of special interest related to PEG-IFN reported during the extended long-term follow-up period of this study.
- Laboratory Safety Data: The laboratory data will be analyzed according to Roche's "International Guideline for the Handling and Reporting of Laboratory Data".
- Growth (weight and height): The continuous growth will be analyzed with residual maximum likelihood, or analysis of covariance. The assumptions of the analysis such as normally distributed residuals will be assessed. If necessary rectifying transformations shall be applied. Growth (height) velocity will be explored.

Pharmacokinetic

- PK parameters (e.g., CL/F V/F, AUC, C_{max}, etc.) of PEG-IFN will be estimated using non-compartmental analysis and/or a population PK modeling approach. All PK parameters will be presented descriptively including arithmetic means, standard deviations, geometric means, coefficient of variation, medians, and ranges.
- The relationship between clinical endpoints and PEG-IFN serum exposure may be explored.

The relationship between pharmacokinetic and pharmacodynamic parameters may be explored.

